Irrespective of discharge location (e.g., home versus skilled nursing facility), the STAR navigator will provide monitoring through phone contact with patient, caregiver, or provider (as appropriate for post-acute care location) at <48 hours, 72-96 hours, and 7-10 days post-discharge. These touchpoints will include medication reconciliation, infection and respiratory symptom monitoring, vitals and weight checks, and confirmation that the patient can make scheduled outpatient appointments. Concerns identified through proactive monitoring will prompt a primary care provider contact for follow-up. If the primary care provider cannot be reached after one attempt, the navigator will contact the hospitalist back-up provider. Following the immediate post-acute interval, the STAR navigator will maintain weekly telehealth touchpoints with patients who remain at high-risk for poor outcome (i.e., any previous positive screen, high-risk comorbid condition [e.g., chronic lung disease, heart failure], or low health literacy) and every third week touchpoints with patients considered low-risk after the immediate post-acute interval. These 90-day post-acute touchpoints will include infection and respiratory symptom check, vitals and weight monitoring, and consideration for repeat outpatient provider visit. Identified concerns will prompt attempts to contact the primary care provider followed by hospitalist back-up provider. The STAR support service will complete 90 days post hospital discharge.

Statistical Analysis

Sample Size Determination: This study is designed to detect a 20% relative reduction in composite 90-day mortality and hospital readmission. The usual care group is indicated to have

roughly 40% combined 90-day mortality and readmission rate. With a total sample size of 4392 patients enrolled over 36 unit-months, we will have 90% power ($\alpha=0.05$) to detect a 20% relative reduction in composite 90-day mortality and hospital readmission.

Statistical Methods

Aim 1: Evaluate the effectiveness of an innovative, virtual nurse navigator implementation strategy to improve post-sepsis care.

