13. Completed care preferences. We will compare the completion of care preferences documents, captured from the electronic health record. We will construct generalized linear mixed-effects models with care preferences document completion as the dependent variable, assessed as a binary outcome at index hospital discharge. The intervention fixed-effect coefficient will compare STAR versus UC conditions, using an intent-to-treat approach.

14. Discharged to hospice care. We will compare the discharged to hospice care from the index hospitalization for sepsis, captured from the electronic health record and hospital discharge records in the enterprise data warehouse. We will construct generalized linear mixed-effects models with discharged to hospice care as the dependent variable, assessed as a binary outcome at index hospital discharge. The intervention fixed-effect coefficient will compare STAR versus UC conditions, using an intent-to-treat approach.

15. Place of death. We will compare the place of death for individuals who die over the 90-day trial interval, captured from the electronic health record and hospital discharge records. We will construct generalized linear mixed-effects models with place of death as the dependent variable, assessed as a categorical outcome at 90 days after hospital discharge. The intervention fixed-effect coefficient will compare STAR versus UC conditions, using an intent-to-treat approach. In addition to primary intent-to-treat analyses, we will conduct modified intent-to-treat analyses excluding sepsis patients 1) who do not survive index hospitalization since STAR is designed to support patients during their transition out of the hospital; and 2) discharged against medical advice since providers do not have the opportunity to deliver full care and prepare the patient for discharge. Based on published data and internal estimates, we expect less than 10% of study patients will die during index hospitalization and fewer than 2% will be discharged against medical advice. We will present results from group comparisons as odds ratios and 95% confidence intervals.

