We do not anticipate substantial missing data because all outcomes are routinely collected variables and utilization is broadly captured within the large integrated system. While utilization may occur outside of CHS, this is not expected to be a major limitation because of CHS market share and accessibility. Specifically, CHS operates three large hospitals in Mecklenburg County, the only acute care hospitals in Anson, Burke, Cleveland, Lincoln, Stanly, and Union counties, where most of this study will be conducted, and more than 40 hospitals in the region overall. Additionally, any utilization that occurs outside the system is anticipated to be non-differentially distributed between groups and thus impact treatment groups equally. Further, internal data indicates nearly 75% of high-risk patients are Medicare-insured and have complete healthcare claims within and outside CHS facilities captured through participation in the ACO managed by CHS. We will leverage this data for subgroup analyses and to explore missing data patterns that can be adjusted using pattern-mixture methods in sensitivity analyses.

All hypothesis tests will be two sided and data will be analyzed using SAS Enterprise Guide v7.1 (Cary, NC) or R v3.5 (Vienna, Austria).

Interim Analysis

Interim analyses will be conducted when 50% of enrollment targets are met and 90-day patient outcomes are obtained. All interim analyses will be presented to the Data and Safety Monitoring Board (a Steering Committee representative, an independent clinician investigator, and an independent biostatistician), who will make a recommendation on continuing the trial as planned or modified. The following analyses will be conducted by the study statistician and provided to the Data and Safety Monitoring Board:

1. Sample size re-estimation

a. Drop-out rate for STAR: We define the drop-out rate for the STAR program to be the rate of nonadherence to the intervention. Non-adherence is defined by those patients who declined, were discharged before contact by STAR staff, and were not able to be contacted after hospital discharge. The population is defined as all patients who were deemed eligible and identified as high risk for readmission or mortality. We propose to assess the drop-out rate in the STAR intervention arm when half of patients have 90-day follow up information available (n=2196). At that time, we will re-estimate the sample size needed for the study using drop-out rates.

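### Equal capture of out-of-system events in both arms is assumed but not checked, and no source is named for deaths in the primary endpoint, while only STAR patients have scheduled contact to day 90

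*Combined protocol and SAP*

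**What the plan says.** **Endpoint.** Under Primary Outcome Variable, a patient with a date of death or an eligible readmission before day 90 is event-positive. Interim Analysis repeats the rule for the event-rate re-estimation. Neither place has a category for unknown status.

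**Outside events.** The missing-data paragraph of Statistical Methods (Aim 1) expects little loss because of the system's market share, and adds that "any utilization that occurs outside the system is anticipated to be non-differentially distributed between groups and thus impact treatment groups equally". It then reports that nearly 75% of high-risk patients have complete claims from inside and outside the system, and says of these: "We will leverage this data for subgroup analyses and to explore missing data patterns that can be adjusted using pattern-mixture methods in sensitivity analyses". Aim 2 accepts that the data warehouse may miss costs arising elsewhere and repeats its analyses in the ACO subgroup.

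**Deaths.** No source is named for the death component of the composite or for 90-day mortality. The only source tied to death is the one for secondary outcome 15, place of death, which is "captured from the electronic health record and hospital discharge records". The Introduction names the data warehouse as a source of clinical outcomes, but for the economic evaluation.

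**Contact.** Study Procedures describes STAR as support by telephone and through the EHR. Contacts fall within 48 hours, at 72-96 hours and at 7-10 days. After that "the STAR navigator will maintain weekly telehealth touchpoints with patients who remain at high-risk for poor outcome", and lower-risk patients are contacted every third week, to day 90 and at every discharge location. Usual care is existing standard activity, with no study contact described.

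**Planned effect.** The usual-care group is expected to have "roughly 40% combined 90-day mortality and readmission rate", and the design targets a 20% relative reduction. On testing: "All hypothesis tests will be two sided".

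**The concern.** Market share is an argument that few events are missed overall. It is not evidence that the same fraction is missed in each arm. Losing the same fraction leaves the relative risk unchanged and costs little power; losing different fractions biases the comparison.

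The intervention gives a reason why the fractions could differ. A navigator in regular contact with the patient, caregiver or facility can learn of a death at home, in a nursing facility or in hospice, or of an admission elsewhere. The navigator works through the EHR, which is the one kind of source the plan links to death. A usual-care patient with the same event may leave no trace in the system.

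The planned remedy does not fit this problem as it stands. Pattern-mixture methods act on values known to be missing, and an unseen outside event is stored as a non-event.

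If STAR events are better recorded, a real benefit is diluted and a null effect can look like harm. The same endpoint drives the interim efficacy test, the futility rule (conditional power below 0.10 under the designed alternative) and the event-rate re-estimation.

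**Working it through.** **Inputs from the documents.** Eight hospitals, one crossing every four months, with enrollment July 2020 to June 2023 (36 months, 9 periods). N = 4392, so 4392/(8 x 9) = 61 per hospital-period. Usual care 40%; STAR 0.80 x 40% = 32%; planned difference 8 points. Two-sided alpha 0.05, stated power 90%.

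**Inputs assumed, because the documents give none.** ICC (0.05 below, with no decay over time). Share p of patients whose only event is an outside death or readmission: 4%, range 2-6%. Capture of those events: 70% in usual care (range 50-80%) and 95% in STAR (range 90-95%).

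**1. The plan's own figure.** Hussey-Hughes variance with I = 8 and T = 9. Treated hospital-periods U = 8 + 7 + ... + 1 = 36; W = V = 1 + 4 + ... + 64 = 204.

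Var = I s2 (s2 + T t2) / [(IU - W) s2 + (U^2 + ITU - TW - IV) t2], with s2 = (1 - ICC) v/61, t2 = ICC x v, and v the mean of the two binomial variances.

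At 40% vs 32%, v = (0.2400 + 0.2176)/2 = 0.2288 and SE = 0.0244. Power = Phi(0.08/0.0244 - 1.96) = 90.7%. ICCs of 0.01, 0.02 and 0.1 give 91.9%, 90.8% and 91.7%. The stated 90% is reproduced under these assumed ICCs.

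**2. Shift with no true effect.** Shift = p x (STAR capture - usual-care capture).
- Central: 0.04 x (0.95 - 0.70) = 1.0 point, or 1.0/8 = 12.5% of the planned effect.
- Low: 0.02 x (0.90 - 0.80) = 0.2 points.
- High: 0.06 x (0.95 - 0.50) = 2.7 points.

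**3. Central case with the planned effect.** Usual care observed: 0.40 - 0.04 x 0.30 = 0.388. STAR observed: 0.32 - (0.80 x 0.04) x 0.05 = 0.3184. Relative risk 0.3184/0.388 = 0.82 instead of 0.80. The step 1 formula gives power of 81.7%.

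**4. Mortality alone (further assumptions: 15% true mortality in both arms, 40% of deaths outside hospital).** Usual care: 0.15 x (1 - 0.40 x 0.30) = 13.2%. STAR: 0.15 x (1 - 0.40 x 0.05) = 14.7%. The apparent ratio is 1.11 with no true effect.

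**5. Equal versus unequal loss.** Here capture is the assumed share of all true events recorded, usual care/STAR, with true rates of 40% and 32%.

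| Capture | Observed rates | RR | Power |
|---|---|---|---|
| 100/100 | 40.0% vs 32.0% | 0.80 | 90.7% |
| 95/95 | 38.0% vs 30.4% | 0.80 | 88.3% |
| 95/98 | 38.0% vs 31.4% | 0.83 | 78.3% |
| 95/100 | 38.0% vs 32.0% | 0.84 | 69.6% |

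With no true effect, 95/100 gives 38% vs 40% (OR 1.09) and a 12.4% chance of a significant result against STAR, instead of 2.5%. The reverse gap, 95/90, gives OR 0.92 and a 12.6% chance of a false finding for STAR.

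**6. What claims could recover.** Suppose claims gave full capture in 75% of patients in both arms, with equal event rates in those with and without claims. Usual care under 95/100 becomes 0.40 x (0.75 + 0.25 x 0.95) = 39.5%. Power returns to 86.8%, and the false-harm chance falls from 12.4% to 3.9%.

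**The case against.** The strongest reply is that the mechanism is inferred. The navigator contacts are described as care: symptom checks, medication reconciliation and provider calls. Nothing says that they feed the endpoint, and the plan calls all its outcomes routine data. If events are extracted passively, extra contact need not change capture. This stands: a reader might infer that navigator reports will make STAR patients event-positive, and the documents do not say so. Equally, nothing rules it out.

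Three other strong readings also fail.
- That the plan treats outside deaths as equally missed: the quoted sentence covers utilization only. The gap on deaths is silence about the source, which is not proof that deaths come from the EHR alone.
- That the claims go unused: they have planned subgroup and sensitivity roles, and exploring missing-data patterns could include a comparison of claims with the warehouse. That comparison is not specified, by arm or otherwise.
- That claims would settle the matter: about 25% of high-risk patients lack them, and the documents do not say that claims hold vital status.

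The assumed gap may also be generous. STAR patients who decline or cannot be reached stay in the arm under intention to treat, and usual care includes standard post-discharge activity. The plan gives specific reasons to expect little outside use: the system runs the only acute hospitals in six counties. The central case moves the relative risk only from 0.80 to 0.82.

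**Conclusion.** The concern holds in a limited form. The documents establish that equal capture is assumed without a check by arm, that no source is named for deaths in the primary endpoint, that scheduled contact to day 90 differs by arm, and that an unseen event is scored as no event. They do not establish that capture will differ.

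If it does differ through navigator contact, the bias most likely runs against STAR: a shift of 0.2 to 2.7 points over the assumed range, 1.0 point in the central case. That would dilute a true effect or suggest harm. A reader might infer a risk of a falsely positive trial, but that would need lower capture in STAR, and the documents give no reason to expect it.

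Every capture figure is an assumption, and the power figures also rest on an assumed ICC. What carries the point is the contrast between equal and unequal loss: the first is nearly harmless, and a gap of a few points in the share of all events recorded is not. The change is inexpensive and should be made. Building claims into the primary endpoint itself is debatable and is not required.

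**What to change.** 1. Name the sources for date of death and for readmission, and use the same passive, arm-independent sources in both arms, including at the interim analysis. Use death-record linkage for date of death.
2. State that information known only through STAR navigator contact or notes cannot make a patient event-positive in the primary analysis.
3. In patients with complete claims, estimate by arm the share of claims-identified eligible readmissions that the warehouse also records.
4. Prespecify, as a key sensitivity analysis in place of pattern-mixture for this problem, a primary-endpoint analysis in those patients that counts an eligible readmission found in either warehouse or claims, identically in both arms.

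If the sponsor prefers to build claims into the primary endpoint, it should first check that claims coverage is stable over calendar time. Time is tied to arm in a stepped wedge, so drifting coverage would itself create unequal capture.

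**Cost.** SAP wording, a death-record linkage and analysis of claims already held; enrollment and care delivery are unchanged. Claims and death-record lag may delay the final dataset by some months and could hold back the interim look. A few true STAR events known only to the navigator would be set aside.

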Introduction

Sepsis survivors represent a vulnerable population with high morbidity, mortality, and hospital readmissions, and strategies to improve transition and recovery are urgently needed. Post-sepsis care recommendations target specific deficits experienced by sepsis survivors; however, these recommendations are infrequently applied. Our STAR program implements evidence-based post-sepsis care recommendations, directed to high-risk sepsis survivors, and delivered using a proactive, nurse navigation process demonstrated to reduce readmissions and costs. This project will evaluate if implementation of the STAR program within a large healthcare system will improve outcomes for high-risk sepsis patients and will generate knowledge of best practices for implementation and dissemination of post-sepsis transitions of care.

The proposed research consists of 1) a pragmatic, stepped-wedge, cluster randomized controlled trial, 2) prospective economic evaluation, and 3) concurrent analyses of the implementation process.

- 1) We will conduct a two-arm, pragmatic, stepped-wedge, cluster randomized controlled trial to test the effects of two post-sepsis care implementation strategies on clinical outcomes. At each four-month interval, one of eight hospitals will be randomly assigned to transition from ARM 1) usual care (UC) consisting of current, standard peri- and post-discharge activities, to ARM 2) STAR program beginning during index hospitalization for sepsis and extending 90 days after hospital discharge.
- 2) Cost analysis will occur through a prospective economic evaluation that uses empirical trial data on healthcare costs, health utilization, and clinical outcomes from the hospital system's data warehouse as inputs to a Markov state transition model for formal cost-effectiveness analysis.

3) The study's implementation will be guided by the Consolidated Framework for Implementation Research. A mixed methods evaluation framework will be used to inform future implementation and dissemination activities.

Primary Objective

The primary objective is to evaluate composite 90-day hospital readmissions and mortality between usual care and the STAR program.

Hypothesis

Patients allocated to receive the STAR program intervention will have lower combined hospital readmission and mortality rates at 90 days post hospital discharge, compared to patients allocated to receive usual care.

Primary Outcome Variable

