All primary and secondary analyses will follow intention to treat approach, such that all patients meeting identical criteria and randomized will be analyzed, regardless of adherence to intervention assignment. This real-world approach will assess intervention effectiveness while limiting selection biases associated with adherence. We will compare the two groups (STAR versus usual care) at baseline for age, sex, race, and comorbidities to assess for balance inferred randomization. The primary outcome is the composite of hospital readmission and mortality at 90 days post hospital discharge. Because hospitals are randomized to STAR in a staggered sequence and the outcome varies at the patient level, we will use a generalized linear mixed-effects model to compare the composite 90-day mortality and readmission primary outcome measure between the intervention conditions, adjusting for clustering effects across multiple levels (e.g., admitting hospital, implementation timing) to include hierarchical data structures. The intervention fixed-effect coefficient will compare STAR versus UC conditions (i.e., UC as reference). We will evaluate covariates for patient (e.g., sex, race, comorbidities, length of stay, discharge disposition [skilled nursing facility, rehabilitation, home]) and organizational factors (e.g., admitting hospital, guideline adherence, urban versus rural setting, implementation timing) to identify any potential differences between study arms. We will include covariates in model if unbalanced between STAR and UC groups. We will also evaluate effect

modification by conducting analyses stratified by these characteristics (e.g., discharge disposition) and by process measures with potential to effect outcomes (e.g., referrals).

Secondary outcomes are described below and will be assessed using the same approach. That is, we will construct generalized linear mixed-effects models, like for the primary outcome analysis, for individual assessments of secondary outcomes and process measures. We will test different distribution parameters to determine the optimal distribution family for each model and outcome variable (e.g., binomial, gamma distributions).

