b. Event rate: We propose to re-estimate the sample size based on the combined 90-day hospital readmission and mortality rates for both patients randomly assigned to STAR and usual care when half of the information is available for the trial (n=2196). We will base the re-estimation on the original 20% relative reduction to determine if more patients are needed to maintain 90% power. We will measure the composite outcome as defined for the primary effectiveness analysis, i.e., we will capture all patients with either

date of death or eligible hospital readmission prior to 90 days post discharge as event-positive.

2. Interim efficacy analysis with 50% information (i.e., 50% of target accrual with 90-day follow up data).

We propose to conduct an interim effectiveness analysis of the primary outcome of composite 90-day hospital readmission and mortality rates once 50% of patients have been accrued and have 90-day outcomes. We will use the Haybittle-Peto procedure with boundary of less than 0.001. No additional interim analyses will be planned until the sample size re-estimation and futility analyses are reviewed and a recommendation is made to continue, stop, or modify the study.

3. Futility analysis/conditional power at 50% complete data information (50% of target accrual with 90-day follow-up data). We propose to conduct a futility analysis at 50% information accrual for the trial. The first futility analysis will be conducted at the same time as the sample size re-estimation based on the drop-out rate. Conditional power is the probability of detecting a difference at the end of the study ($p<0.05$) given the current data trend. We will estimate conditional power under the null hypothesis of no difference, the designed alternative of 20% relative reduction, and the current observed trend. A recommendation would be made to stop the study for futility if the conditional power is less than 0.10 for the designed alternative.

**Aim 2: To assess the cost-effectiveness of virtual nurse navigator-driven STAR program
Within-trial Incremental Cost Effectiveness Ratio.**

We will estimate Incremental Cost Effectiveness Ratio (ICER) of STAR versus UC using data derived during the study interval as a measure of benefit to the hospital system. We will estimate ICER as incremental costs divided by incremental QALYs. The intervention group beta weight from cost model will be divided by the intervention group beta weight from QALYs model.

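### The interim re-estimation treats STAR non-adherence as drop-out although ITT keeps those patients, does not reconcile items 1a and 1b, and ignores where added patients can fall in the stepped-wedge calendar

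*Combined protocol and SAP*

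**What the plan says.** All places are in the combined protocol and SAP.

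- **Interim Analysis, item 1a:** "We define the drop-out rate for the STAR program to be the rate of nonadherence to the intervention". Non-adherers are patients who refuse, who leave hospital before STAR staff reach them, or who cannot be reached afterwards. With 2196 patients followed to 90 days, "we will re-estimate the sample size needed for the study using drop-out rates". No formula is given.
- **Statistical Methods, Aim 1:** the analysis is ITT, so "all patients meeting identical criteria and randomized will be analyzed, regardless of adherence to intervention assignment". The same section expects little missing outcome data.
- **Interim Analysis, item 1b:** "We will base the re-estimation on the original 20% relative reduction to determine if more patients are needed to maintain 90% power".
- **Sample Size Determination:** "This study is designed to detect a 20% relative reduction in composite 90-day mortality and hospital readmission". The text states no adherence level and no ICC.
- **Interim Analysis, item 3:** the futility rule uses "the designed alternative of 20% relative reduction".
- **Interim Analysis, opening:** the results go to the monitoring board, "who will make a recommendation on continuing the trial as planned or modified".
- **Randomization and Recruitment Plan:** one hospital crosses over every four months and stays on STAR to the end. Eligible patients at all eight hospitals are included. Enrolment is expected from July 2020 through June 2023, and all activity is expected to end by December 2023.

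**The concern.** Drop-out in a sample size calculation normally means patients whose outcome is lost. The patients counted in item 1a are not lost: they are analysed in the STAR arm with their 90-day outcome. A calculation that treats them as missing answers the wrong question. What matters is whether the ITT effect is smaller than the one the trial was sized for, and item 1b rules that out by holding the effect at 20%. The two items could return different sample sizes, and nothing says which governs.

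Both items also speak of more patients as if each were worth the same. In a one-way stepped wedge, a patient's value depends on the period in which he or she is enrolled. The board could therefore receive a sample size said to maintain 90% power that does not do so, at the last point when the remaining schedule could still be changed.

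**Working it through.** **1. The plan's own figure.** Inputs from the documents: 40% under usual care, 20% relative reduction (so 32%), two-sided 0.05, 90% power, N = 4392, eight hospitals, four-month steps, 36 months.

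- Individual randomization: n per arm = [1.960√(2 × 0.36 × 0.64) + 1.282√(0.24 + 0.2176)]² / 0.08² = 755, total 1510. The implied design effect is 4392/1510 = 2.91.
- Periods: 36/4 = 9. Cell size: 4392/(8 × 9) = 61.
- The ICC is not given, so 4392 cannot be derived from the documents alone. Assumed model: Hussey–Hughes with random hospital and fixed period effects. Cell means within a hospital have covariance ρσ², plus (1−ρ)σ²/m on the diagonal. σ² = p(1−p), with p at 0.40 or at the mean of the two rates. Power = Φ(δ/√v − 1.960), with δ = 0.08.
- For ICC 0.005–0.10 this gives 89.3–93.5%, which is compatible with the stated 90%.

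**2. Calendar, under even accrual.** 4392/36 = 122 patients a month. 2196/122 = month 18, plus about 3 months of follow-up = month 21. Crossovers fall at months 4, 8, …, 32, so those at 24, 28 and 32 remain. Past periods cannot be enlarged, and because all eligible patients are already taken, more patients means more months. The stated dates leave about 6 − 3 = 3 months after June 2023, or 3 × 122 = 366 patients.

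**3. What non-adherence does.** Let d be the non-adherent share and k the share of the effect that non-adherers keep. The number analysed does not change. The ITT effect becomes 8 points × [1 − d(1−k)].

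The documents give no d. Illustration with d = 20% and k = 0, if the 20% reduction assumes full adherence: 8 × 0.8 = 6.4 points. Starting from exactly 90% power (1.960 + 1.282 = 3.242):

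- No added patients: Φ(3.242 × 0.8 − 1.960) = 73.7%.
- N/(1−d) = 4392/0.8 = 5490 (+1098): Φ(3.242 × 0.8/√0.8 − 1.960) = 82.6%, even with every added patient at full value.
- Dilution formula N/(1−d)² = 4392/0.64, about 6862 (+2470): 90%, again only at full value.

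N/(1−d) is an assumption of this review. The plan gives no formula.

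**4. Placement.** Information per added patient = (v before / v after − 1) / (added/4392). Ranges are over ICC 0.005–0.10; the powers take d = 20% and k = 0.

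| Where added | Information per patient, +1464 | Power, +1098 | Power, +2470 |
|---|---|---|---|
| Periods 7–8 lengthened | 76.2–82.9% | 80.6–85.6% | 86.3–90.4% |
| After month 36, all STAR | 28.6–57.6% | 77.9–81.7% | 81.5–85.1% |

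If non-adherers keep half the effect, +1098 after month 36 gives 86.7–89.8%. For N/(1−d) to restore design power, k must be about 0.54–0.57 in periods 7–8, or 0.66–0.82 after month 36.

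**5. Item 1b alone.** Assume a usual-care rate of 30–35%, ICC 0.01–0.05 and variance at the mean of the two rates. An N that would give 90% if spread over the whole design gives only about 84–88% if the extra patients come after month 36.

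**6. Sensitivity.**

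- Decaying correlation: with cluster autocorrelation 0.8, design power itself is about 58–93% over the same ICCs.
- Very small ICC: at 0.001, design power is 97%, and +1098 after month 36 (d = 20%, k = 0) gives 86–87%.
- Unequal hospitals (any three at two or three times the size of the others): information per added patient ranges over 16–102% after month 36 and 55–147% in periods 7–8. Periods 7–8 are better in at least 271 of 280 settings.

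**The case against.** Four objections deserve weight.

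- **Using non-adherence in an ITT sample size is legitimate.** This stands. A reader might infer that the 20% is simply the ITT effect, so that item 1a should add nothing and be deleted. Several places lean that way: the hypothesis reads "Patients allocated to receive the STAR program intervention will have lower combined hospital readmission and mortality rates at 90 days post hospital discharge", the sample size section makes no adherence allowance, and the futility rule takes 20% as the design alternative. None of them excludes a third reading, that 20% is the ITT effect expected at some anticipated but unstated adherence. On that reading a check against worse adherence is useful. The fault lies in treating non-adherence as loss and leaving its reference level unstated.
- **The board is not left blind.** A reader might infer that it has no means of judging the new sample size. Item 3 gives it conditional power under the null, the designed effect and the observed trend, and the observed trend already contains any dilution so far. The board includes an independent biostatistician and only recommends. This stands, but conditional power is noisy at half information and yields no sample size.
- **The plan states no inflation formula.** A reader might infer that it would enrol 1098 unneeded patients. That needs both an assumed d of 20% and N/(1−d) applied to the whole trial. Applied only to the STAR half it would be 2196/0.8 − 2196 = 549. Neither figure is the plan's.
- **Late patients are not always worth less.** The unequal-hospital runs include exceptions. The statement holds usually, not in every setting.

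**Conclusion.** The point holds as a matter that should be corrected. Read literally, item 1a brings non-adherence in as lost sample, which contradicts the ITT analysis. Items 1a and 1b are not reconciled on the effect size. Both overlook that added patients can fall only in lengthened remaining steps or after month 36.

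The placement problem does not depend on the drop-out label. In the illustrative model, patients added after month 36 bring roughly a third to three fifths of their nominal information. If the 20% assumes full adherence and non-adherers gain nothing, a simple inflation at d = 20% leaves power at about 78–86% depending on placement, not 90%.

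These sizes rest on equal hospitals, even accrual, an assumed ICC and constant within-hospital correlation. Power would be lower if that correlation decays over time. A reader might infer that 4392 is itself too small. The documents do not support that, since they give no ICC and the figure is compatible with 90% under the constant-correlation model. The primary analysis is not affected.

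**What to change.** - **Item 1a:** do not treat non-adherence as loss of sample. State the adherence at which the 20% ITT effect is assumed to hold. If observed adherence is at or above that level, make no adjustment and report it descriptively. If it is lower, compute power at the correspondingly diluted ITT effect, with complete loss of effect in non-adherers as the worst case.
- **Items 1a and 1b together:** use one calculation that combines the observed event rate and any dilution. Base it on the stepped-wedge variance with period effects, a stated ICC, a sensitivity analysis for decaying correlation, and the calendar positions that added patients could actually occupy.
- **Report to the board:** if that calculation does not reach 90%, give the achievable power alongside the conditional power in item 3, not a sample size said to maintain 90%.

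The cost is a little more interim analysis work and possibly a less favourable stated power. If remaining steps were lengthened, later crossovers and perhaps the expected end dates would move.
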